**Human Subject Research**

Does the protocol meet the federal definition of research? For help determining the type of research you are conducting, see the DHHR Human Subject Regulations Decision Charts at <http://www.hhs.gov/ohrp/policy/checklists/decisioncharts.html>.

Yes

Does the research involve living person(s)?

Yes

Will information from individual person(s) be collected as part of this research?

Yes

**Funding Source**

Is there a secured funding source?

No

**Locations of Research**

Select the location(s) where the research will be conducted. At least one location must be selected.

Ruby Memorial Hospital or Other WVU Healthcare Site

Select the location(s) where the research will be conducted. At least one location must be selected.

WVU Campus

Will the research take place at an off campus location?

No

Will this study require an Inter-Institutional Authorization Agreement (IAA)?

No

**Design**

Please provide a lay summary (written at 6th grade level) that includes a statement about the purpose and the general aims of the research.

Dysphagia (difficulty swallowing) is common following anterior cervical spine surgery. Studies have documented persistent swallowing difficulty up to two years postoperatively. The long term objective is to change the treatment paradigm for cervical spine surgery to minimize dysphagia and associated complications. The specific aims are to identify the effect of a single dose of perioperative steroid on dysphagia and to develop a treatment protocol for the frequency of perioperative steroids needed to reduce dysphagia. This is a prospective, randomized, placebo-controlled study. Patients will be given a single dose of dexamethasone or normal saline intratoperatively and then assessed at multiple time points up to one year. The research question is what is the effect of a single dose of perioperative steroid on dysphagia after anterior cervical spine surgery? The survey instruments used to determine difficulty swallowing include the Bazaz, Dysphagia Short Questionnaire, and EAT 10. To administer the Bazaz instrument, the study coordinator will ask the subject if he/she has difficulty swallowing liquid food and give the options 'none', 'rare', 'present all the time'. The options for solid food are 'none', 'rare', 'occasional only with specific foods', or 'frequent majority of solids'. The options on the left side of the questionnaire determine the level of difficulty. If a subject has no difficulty swallowing both liquid and solid food, 'none' will be chosen. The level of difficulty swallowing is determined by the highest difficulty, e.g. if a subject had no difficulty swallowing liquid food and has rare difficulty swallowing solid food, 'mild' will be chosen. If the subject has no difficulty swallowing liquid food but has frequent difficulty swallowing solid food, 'severe' will be chosen.

Fully describe all procedures to be performed, from start to finish, numbering your procedures 1,2,3 or A, B, C (e.g., 1. Recruiting, 2. Consent, 3. Collecting data, 4. How findings will be shared, etc.).

1. Potential subjects will see Drs. [name], [name], [name], [name] or [name] at their visit prior to elective anterior cervical spine surgery at the Spine or Neurosurgery Clinic. 2. Subjects will be told about the study at this visit, all questions will be answered by the surgeons and the research coordinator, all surveys that need to be completed will be shown to the potential subjects and they will be given the opportunity to consent. 3. If consented, the subject will be asked to complete baseline surveys (Bazaz, EAT-10, and Dysphagia Short Questionnaire) at this visit. The subject will also complete Standard of Care Patient Reported Outcome Measures (PROMS) at this visit. 4. The subject will be randomized to receive either single dose steroid (dexamethasone) or saline (placebo) prior to surgery. The dose is calculated based on body weight group will receive 0.3 mg/kg of intravenous dexamethasone (experimental group) 0.3 mg/kg saline (control group). The subject will not be charged for dexamethasone or saline. 5. The subject will undergo anterior cervical spine surgery per standard of care. 6. After administration of the antibiotics in the operating room, the single dose of steroid or saline will be given by the anesthesia team, who are blinded to the group assignment, via an intravenous bag (study drug) prepared by the investigational pharmacist, the only person who knows the group assignment. 7. The surgeon, patient, and research team are blinded to the group assignment. 8. The subject will be administered the surveys by phone call or in the hospital by the research coordinator on Day 1. 9. On Day 2, if the subject is still hospitalized, surveys will be administered by the research coordinator in the hospital or via phone call. 10. Following Day one surveys, and if the subject has been discharged, the subject will be called to complete the answers to the surveys via phone call at Day 2, Week 1, Week 2, Month 1, Month 3, Month 6 and Month 12. At Month 12, the subject will be asked to also complete standard of care PROMS. If the subject is in the clinic for follow up at the designated time frame for survey administration, the surveys will be completed in the clinic. If the subject is not in clinic at Month 12, the PROMS will be completed via phone call. 10. At the end of the study, all subjects will be called or mailed a letter indicating the group assignment they had been in. 11. Study Results will not be shared with the subjects.

Please describe the investigational procedures that will be performed throughout the duration of the study.

Randomization to steroids or no steroids for anterior spinal fusion subjects and completion of the Bazaz, Short Dysphagia Questionnaire and EAT-10 survey.

Please describe the standard of care procedures that will be performed throughout the duration of the study.

Everything outside of the randomization.

Will you be assigning or randomizing participants to groups or conditions (e.g., control, placebo)?

Yes

Describe the group assignment.

Random assignment to receive either one dose of steroid or one dose of saline (Placebo) during the first hour of surgery.

Does the research involve surveys/interviews/questionnaires? If so, attach a copy of the interview/survey questions on the Notes & Attachments page.

Yes

Will you be asking any questions that are likely to distress your subjects (e.g., questions about abuse, trauma, or suicide ideation)? If so, attach counseling services referral list on the Notes & Attachments page.

No

Describe what is known about this topic and why this study is needed. Please include at least two reference citations to support your rationale.  
See lit review and scientific rationale under Notes and Attachments.

What method are you going to use to analyze the data?

Swallowing symptoms will be measured using the patient reported Bazaz Dysphagia Scale, EAT-10 survey, and the Dysphagia Short Questionnaire. Swallowing data will be obtained pre-operatively, one and two days post-operatively and then one week, two weeks, four weeks, three months, six months, and one year post-operatively. Scores from the Bazaz Dysphagia Scale and the Dysphagia Short Questionnaire from the two groups will be compared at the various time points using the Mann-Whitney U test. Power and sample size calculations are based on the presence or absence of dysphagia at two weeks. Based on a literature review, we postulated that 50% of the patients in the control group would experience mild, moderate, or severe dysphagia. If that figure can be improved to the point where just 20% of the patients are similarly affected then that, in our opinion, would represent clinical success. Under the above scenario, 32 patients in each group would give us 81% power to reject the null hypothesis. Assuming a dropout rate of 20% our total sample size for the study is 80. Statistical significance is set at  $p < 0.05$ . We plan to analyze the data in three ways. First, we will look at the time-to-event where the event is "no dysphagia" in a discrete time survival model. Second, we will use a repeated measures ordinal categorical model to assess the effect of steroid/control in a generalized linear model. Lastly, we will compare the data from this study with that of our previous three-dose model to assess any difference in the degree of impact of the two dosing regimens.

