### Subjects

Indicate the maximum number of subjects to be enrolled or medical records to be reviewed at all sites by the WVU or VAMC research team.

80

Provide a rationale for choosing your sample size.

Scores from the Bazaz scale, the EAT-10, and the Dysphagia Short Questionnaire from the two groups will be compared at the various time points using the Mann-Whitney U test. Statistical significance is set at  $p<0.05$ . With a power of 0.80 and a clinical meaningful difference of 30% in scores, an estimated 32 patients per group is needed. However, based on a recent unpublished study at our institution, we expect a dropout rate of approximately 20%, and therefore plan for a total sample size for this study of 80 patients.

State the requirement(s) to become a participant in the study (e.g., age range, sex, language spoken, class enrollment/ranking).

Ages 18-80; undergoing elective ACDF, hybrid constructs, corpectomies, disc arthroplasty surgery

Explain why selection of participants will be equitable addressing gender, ethnicity, and/or race of subjects.

No one will be excluded based on gender, ethnicity or race. Exclusion criteria include: < 18 years of age; major trauma or neoplastic or infectious conditions requiring surgery. Also excluded will be patients undergoing anterior-posterior operations, those with a history of previous anterior cervical spine surgery, any patient requiring a halo vest, patients on chronic steroids, and patients remaining intubated post-operatively, and women who are pregnant.

In outline format and chronological order, describe what will be done to identify and recruit participants (e.g., A, B, C or 1, 2, 3).

1. Potential subjects will see Drs. [name], [name], [name], [name] or [name] at their History and Physical visit prior to elective anterior cervical spine surgery at the Spine Center. 2. Subjects will be told about the study at this visit, all questions will be answered by the surgeons and the research coordinator, all surveys that need to be completed will be shown to the potential subjects and they will be given the opportunity to consent. 3. If consented, the subject will be asked to complete baseline surveys (Bazaz, EAT-10 and Dysphagia Short Questionnaire) at this visit. 4. The subject will be randomized to receive either single dose steroid (dexamethasone) or saline (placebo) prior to surgery.

Will any of the subjects be less than 18 years old?

No

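### Pre-operative swallowing scores are collected before randomisation, but no planned analysis names them as a covariate: a possible loss of precision, not bias

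*Combined protocol and SAP*

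**What the plan says.** All quotations are from the Combined protocol and SAP.

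- **Collection.** Step 3 of the Design procedures reads: "If consented, the subject will be asked to complete baseline surveys (Bazaz, EAT-10, and Dysphagia Short Questionnaire) at this visit". The recruitment steps in the Subjects section repeat this ("If consented, the subject will be asked to complete baseline surveys (Bazaz, EAT-10 and Dysphagia Short Questionnaire) at this visit") and place randomisation in the next step.
- **Timing.** The analysis answer in the Design section lists the pre-operative visit among the measurement times: "Swallowing data will be obtained pre-operatively, one and two days post-operatively and then one week, two weeks, four weeks, three months, six months", followed by one year.
- **Group comparison.** The Design section says: "Scores from the Bazaz Dysphagia Scale and the Dysphagia Short Questionnaire from the two groups will be compared at the various time points", by Mann-Whitney U. The sample size rationale in the Subjects section adds the third instrument: "the EAT-10, and the Dysphagia Short Questionnaire from the two groups will be compared at the various time points using the Mann-Whitney U test".
- **Models.** The time to absence of dysphagia is to be analysed "in a discrete time survival model. Second, we will use a repeated measures ordinal categorical model to assess the effect of steroid/control". No covariate is named for the first model, and only treatment arm for the second.
- **Sizing endpoint.** "Power and sample size calculations are based on the presence or absence of dysphagia at two weeks".
- **Eligibility.** The exclusions include "those with a history of previous anterior cervical spine surgery, any patient requiring a halo vest, patients on chronic steroids, and patients remaining intubated", along with trauma, tumour, infection, combined anterior-posterior surgery and pregnancy. Existing dysphagia is not among them.

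**The concern.** Patients with swallowing difficulty before surgery may enter the trial, and such difficulty could plausibly predict scores afterwards and the time until dysphagia is absent. If it does, part of the between-patient variation could be removed with a measurement already being taken. A Mann-Whitney test at each visit cannot do that, and the text on the two models does not say that they will.

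There is also a question of pre-specification. The plan does not say whether the pre-operative score is a covariate, one of the repeated responses, or unused. Left open, that choice could be made after results are known. With 32 evaluable patients per arm and enrolment capped at 80, a few points of power at no cost to patients are worth having.

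**Working it through.** **Inputs from the documents.** Any dysphagia at two weeks 50% (control) versus 20% (steroid); 32 per arm; stated power 81%; significance level 0.05, sidedness not stated; 20% dropout; total 80.

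**Inputs that must be assumed.** Prevalence of dysphagia before surgery, and the latent correlation r between the pre-operative and two-week states. Ranges are used for both.

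**Step 1: the plan's own figure.** Power = Φ[(d − z·SE0)/SE1], with d = 0.30.
- SE0 = √(2 × 0.35 × 0.65/32) = 0.1192
- SE1 = √((0.25 + 0.16)/32) = 0.1132
- One-sided (z = 1.645): (0.300 − 0.196)/0.1132 = 0.92, power 82.1%
- Two-sided (z = 1.960): (0.300 − 0.234)/0.1132 = 0.59, power 72.1%

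The stated 81% is approximated one-sided (solving for 81% gives 32 per arm), not two-sided. The total follows: 64/0.80 = 80. Neither figure uses baseline information. Sidedness is a separate matter; here it only fixes the starting point.

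**Step 2: why the usual formula overstates the gain.** For a continuous score, adjustment multiplies the variance by 1 − r²: 0.91 at r = 0.3 and 0.75 at r = 0.5. Here most patients may have no dysphagia at baseline, so much of the latent correlation is lost. In simulation with latent r = 0.5, the correlation between yes/no baseline status and yes/no two-week status in the control arm was 0.225 at 10% prevalence and 0.292 at 25%. The factors become 1 − 0.225² = 0.949 and 1 − 0.292² = 0.915, a variance reduction of about 5% to 9%, not 25%.

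**Step 3: power by simulation.** Each simulated trial (32 per arm, 50% versus 20%, two-sided 5%) was tested by logistic likelihood ratio with and without a four-level baseline score. There were 4,000 or 6,000 trials per setting, and the paired Monte Carlo standard error was 0.2 to 0.5 points. Gains in power points are below; a range shows two separate runs.

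| Baseline prevalence | r = 0 | r = 0.3 | r = 0.5 | r = 0.6 |
|---|---|---|---|---|
| 2% | not run | +0.3 | +0.5 | +1.2 |
| 5% | not run | +0.1 | +1.6 | +2.0 |
| 10% | 0.0 | +1.0 to +1.4 | +2.4 to +2.5 | +3.2 to +4.1 |
| 20% | +0.4 | +1.6 | +3.5 to +4.0 | +5.6 to +6.7 |

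A further run gave about 0 to +2.6 points at 2-5% prevalence. At 10-20% it gave +0.6 to +2.0, +2.3 to +3.4 and +4.2 to +6.4 for r = 0.3, 0.5 and 0.6. Its rejection rate with no treatment effect was not raised by adjustment.

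**Step 4: the two planned models.** These results are indicative only. They come from one set of simulations and need assumed dysphagia rates at every visit other than week 2. Prevalence was 10% and 20%.
- *Repeated-measures ordinal model, two-week contrast.* Two-sided gains were +0.8 to +1.5 (r = 0.3), +2.8 to +4.6 (0.5) and +4.3 to +7.8 (0.6), with −0.4 to 0.0 at r = 0. One-sided gains were +0.2 to +1.0, +2.4 to +3.3 and +3.6 to +5.1, with −0.4 to −0.2 at r = 0.
- *Discrete-time survival model, critical values set from the simulated null.* At r = 0.3, power rose from 79.6% to 80.8% (10% prevalence) and from 79.0% to 81.5% (20%). At r = 0.5, it rose from 78.5% to 83.8% and from 75.8% to 83.2%. At r = 0.6, it rose from 75.8% to 85.0% at 10%; the 20% setting was not completed.

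**Step 5: sparse baselines.** If every patient with dysphagia at baseline has the same two-week outcome, the baseline coefficient has no finite estimate. With a treatment effect present, this happened in about 7-20% of simulated trials at 10% prevalence and 32-53% at 5%. The arm effect can still be estimated.

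**The case against.** The strongest reply is that nothing in the plan is wrong. The unadjusted comparisons are valid, no stated figure depends on baseline, and a short answer on a review form that names model families need not list covariates. The pre-operative visit is among the measurement times, so the repeated-measures model may take that score as a response and recover some precision. The gain could also be negligible: with 2-5% of patients affected before surgery it is at most about 3 points, and eligibility limited to elective patients without previous anterior cervical surgery makes a low prevalence plausible. Sparse baselines also make adjustment less simple than adding a term.

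Most of this stands. It limits the size of the point and adds a condition to the fix. It does not remove the point: the role of the pre-operative score is unstated, and settling it in advance costs little.

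Three stronger readings should be resisted.
- A reader might infer that the comparisons are biased. Randomisation rules that out as a consequence of not adjusting.
- A reader might infer that the investigators have decided to ignore baseline. The documents are silent, which is weaker.
- A reader might apply 1 − r² and expect two-sided power to rise from 72% to 84% at r = 0.5. That formula is for a continuous score and does not carry over to a coarse scale on which most patients may start at none.

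**Conclusion.** The point holds as one of efficiency and pre-specification. Scores on all three instruments are requested before randomisation, the Mann-Whitney comparisons do not use them, and neither model names them as a covariate.

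For the two-week endpoint behind the sample size, at two-sided 5%, adjustment is worth:
- about 0 to 3 points of power if 2-5% of patients have dysphagia before surgery;
- about 0.6-2 (latent r = 0.3), 2-4 (0.5) or 4-6 (0.6) points if 10-20% do, with single runs at r = 0.6 from 3.2 to 6.7;
- a change within about half a point of zero if baseline is uninformative.

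Prevalence and correlation are assumptions, so the documents cannot show where in this range the trial lies. The balance still favours adjustment, because the possible loss is negligible and the possible gain is modest but real. Confidence is medium.

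**What to change.** Before unblinding, add the following to the analysis text.

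1. In both the repeated-measures ordinal model and the discrete-time survival model, include the patient's own pre-operative score on the same instrument as one numeric covariate. Do not use a change score, and do not treat the pre-operative score as a post-randomisation response.
2. Keep Mann-Whitney U as an unadjusted supporting analysis at the post-operative visits.
3. Fill a missing pre-operative score with the mean over both arms, so that no patient is dropped. With 10% of baselines missing and filled this way, the simulated ordinal-model gains at r = 0.5 were still +3.2 (10% prevalence) and +5.0 points (20%).
4. State a fallback for when few patients have baseline dysphagia and the baseline coefficient is not finite, for example a penalised likelihood fit or the unadjusted model.
5. Optionally, add a baseline-adjusted analysis of any dysphagia at two weeks, reported as a standardised risk difference with its confidence interval.

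The cost is a few lines of text and the sparse-baseline fallback. Odds ratios from the adjusted models become conditional on baseline; the optional risk difference would give a marginal figure beside them. No patients, visits or questionnaires are added.

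### The trial is sized on any dysphagia at two weeks, but no listed analysis tests that proportion, none is named primary, and the stated 81% power at 32 per group fits only a one-sided test

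*Combined protocol and SAP*

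**What the plan says.** Under the analysis-method question in the Design section, the sample size rests on a binary endpoint at one visit: "Power and sample size calculations are based on the presence or absence of dysphagia at two weeks". The inputs are a control rate ("we postulated that 50% of the patients in the control group would experience mild, moderate, or severe dysphagia") and a target ("If that figure can be improved to the point where just 20% of the patients are similarly affected"), an improvement that "in our opinion, would represent clinical success". The result is "Under the above scenario, 32 patients in each group would give us 81% power to reject the null hypothesis". Allowing for 20% dropout, 80 are to be enrolled. Significance is p<0.05, with no statement of one or two sides.

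The same answer lists the analyses:

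- "Scores from the Bazaz Dysphagia Scale and the Dysphagia Short Questionnaire from the two groups will be compared at the various time points", by Mann-Whitney U.
- "We plan to analyze the data in three ways": a discrete-time survival model with absence of dysphagia as the event; a repeated-measures ordinal model; and "Lastly, we will compare the data from this study with that of our previous three-dose model".

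The Subjects section (sample-size rationale) reaches the same 32 per group and total of 80 at 0.80 power. It describes the basis as a 30% difference in scores, beside the Mann-Whitney test, and adds EAT-10 to the instruments tested.

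**The concern.** The quantity that sized the trial and defines clinical success is a difference between two proportions at week two. No listed analysis estimates or tests it. The Mann-Whitney test of the Bazaz score at that visit is the nearest, but it responds to severity among the affected as well as to whether dysphagia is present. The survival model uses dysphagia status but addresses time to resolution.

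No endpoint, visit, instrument or model is named primary. One significance level covers 16 post-operative Mann-Whitney tests (2 instruments × 8 visits), or 24 with EAT-10, plus two models and a comparison with another study. If the two-week result, another visit and a model point different ways, nothing says which one answers the research question.

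The stated power raises a second issue. If the intended test is two-sided, the chance of missing the sponsor's own success criterion with 32 evaluable per group is about 27–28%, not 19%.

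**Working it through.** **Inputs (Design section).** p₁ = 0.50, p₂ = 0.20, difference 0.30, n = 32 per group, α = 0.05, dropout 20%. Sidedness is not given, so both are tried.

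**Standard errors at n = 32.** The mean proportion is 0.35.
- Null (pooled): SE₀ = √(2 × 0.35 × 0.65 / 32) = 0.1192
- Alternative: SE₁ = √((0.25 + 0.16) / 32) = 0.1132

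**Power = Φ[(0.30 − z × SE₀) / SE₁].**
- One-sided, z = 1.645: (0.30 − 0.1961) / 0.1132 = 0.918, power 82.1%.
- Two-sided, z = 1.960: (0.30 − 0.2337) / 0.1132 = 0.586, power 72.1%.

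The closest match to 81% is one-sided with the pooled SE used throughout: 0.30 / 0.1192 − 1.645 = 0.871, power 80.8%. The two-sided counterpart is 71.1%.

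| Method, n = 32 | One-sided | Two-sided |
|---|---|---|
| Pooled normal | 82.1% | 72.1% |
| Arcsine | 82.4% | 73.0% |
| Exact power, Pearson chi-square | 82.1% | 73.4% |
| Unpooled normal | 84.3% | 75.5% |
| Continuity-corrected | 73.9% | 62.2% |
| Fisher | 74.8% | 64.4% |

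No two-sided method comes within 2 points of 81%.

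**Sample size.** The dropout step is right: 64 / 0.8 = 80. Two-sided pooled power by evaluable number per group is 77.2% at 36, 79.5% at 38, 80.5% at 39 and 81.6% at 40 (exact chi-square at 40: 81.7%). At 32 per group, 80% two-sided power would need 50% to fall to about 17.5% rather than 20%.

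**How far the two-week Mann-Whitney stands in for the proportion test.** Simulation of a four-level Bazaz score, 32 per group, 50% against 20% affected, two-sided 5%, 40,000 trials per setting. The mild/moderate/severe splits among the affected are assumptions, because the documents give none. The last column is how often the Mann-Whitney and chi-square tests differ on significance.

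| Control split | Steroid split | Mann-Whitney power | Tests disagree |
|---|---|---|---|
| 60/30/10 | 60/30/10 | 70.7% | 5.9% |
| equal thirds | equal thirds | 70.4% | 6.8% |
| 40/40/20 | 80/15/5 | 82.3% | 9.4% |
| 70/25/5 | 20/40/40 | 51.7% | 21.9% |

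With 50% affected in both arms but milder cases on steroid (40/40/20 against 80/15/5), Mann-Whitney rejects in 12.2% of trials and chi-square in 6.2%. The two tests therefore answer related but different questions.

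**Multiplicity, conditional.** The documents do not say that any single p<0.05 would count as success. If it were read that way, the simulated chance of at least one false positive is 15–51% for 16 tests and 17–63% for 24. This assumes correlations of 0.5 to 0.9, either uniform or decaying across visits; the documents give none.

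**The case against.** Six points can be made for the plan.

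1. **Sidedness is not stated.** The 81% is then not a proven arithmetic error, since a one-sided test reproduces it closely. This stands. What is certain is that the sidedness must be declared, and that a two-sided reading makes the figure wrong.
2. **The 20% loss covers a year.** Part of it may fall after week two, so the evaluable number at the sizing visit could lie between 32 and 40 and two-sided power between 72% and 82%. This also stands. But the plan attaches its 81% to 32 per group, and at that number it does not hold two-sided.
3. **The primary endpoint is implicit.** The plan fixes a visit, a definition and a success difference, and a Bazaz Mann-Whitney is due at that visit. With equal severity in both arms the two tests seldom disagree. An implicit choice still leaves the models, the other visits and the other instruments with equal standing. Announcing three ways of analysis could even mean that the models lead, in which case the trial was not sized for its leading analysis.
4. **The severity splits and correlations are assumed.** True; they show sensitivity only, and the conclusion does not depend on them.
5. **The wording in Subjects is probably a loose restatement of 50% minus 20%.** Likely so, but a reader cannot tell from it whether the endpoint is a score or a proportion.
6. **Attachments not supplied might name a primary analysis.** They are cited for the literature review and the safety monitoring plan, whereas the form's analysis question is answered in Design. The finding is limited to the text supplied.

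**Conclusion.** The concern holds. In the text supplied, the endpoint that sized the trial is not tested by any listed analysis, and no analysis is primary. That conclusion comes from the text alone and is the main reason to act before unblinding.

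The power figure must also change or be explained. The 9-point gap between the stated 81% and 72% two-sided assumes 50% against 20%, a two-sided 5% test and 32 evaluable per group. It closes only if none of the 40 per group is lost by week two, or if the test is one-sided and the plan says so.

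**What to change.** Use the same text in the Design and Subjects sections:

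1. Name any dysphagia at two weeks (Bazaz mild, moderate or severe, against none) as the sole primary endpoint. Compare the randomised groups by risk difference with 95% CI and a two-sided 5% Pearson chi-square test.
2. Make all other visit-by-instrument tests, both models and the three-dose comparison secondary. Either adjust them by Holm's method or report estimates with CIs and no significance claim.
3. Restate two-sided power as about 72–73% with 32 evaluable per group and about 82% if all 40 are evaluable; or state and justify a one-sided test.
4. In Subjects, replace the difference in scores with the two proportions, 50% and 20%.

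**Cost.** Wording only, with no added enrolment. Fewer results may be called significant, and the stated power is less favourable. The chi-square test can reach an exact size of 6.0% at 32 per group (5.2% when both rates are 35%). If strict 5% control is wanted, Boschloo's exact test stays at or below 4.7% at 32 per group, with power of 72% there and 81% at 40. The sponsor could make the ordinal or survival model primary instead, but would then have to re-size for it. Keeping 80% two-sided power after 20% loss would need 39 evaluable per group: 39 / 0.8 = 48.75, so 49 per group and 98 in total. That is optional and not part of this fix.

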### **Potential Benefits**

Is there any known benefit to the individual subject as a result of participating in the research? Payments to subjects should not be included in this section, but addressed in the Payments/Reimbursements section.

Potential benefit is less difficulty swallowing if the subject is assigned to the steroid group.

Describe the potential benefit(s) to society and/or scientific / medical knowledge of the planned work.

The results of this study will provide evidence for the use of steroids as a treatment for reducing the incidence and severity of dysphagia among patients undergoing anterior cervical spine surgery. A recently performed study at our institution has promising results from a three-dose regimen of steroids.

Similarly, two recent clinical studies have also shown decreased dysphagia with a multi-dose steroid regimen. If the hypothesis of this proposal is supported, the use of a single dose of perioperative steroid specifically lends itself well to application in patients undergoing these procedures in outpatient surgery centers, improving the safety of such procedures.

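### Dysphagia is counted without reference to the patient's own pre-operative grade, so dysphagia present before surgery is mixed with dysphagia after it

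*Combined protocol and SAP*

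**What the plan says.** The Design section, in its answer on analysis method, states "Power and sample size calculations are based on the presence or absence of dysphagia at two weeks". For that calculation "we postulated that 50% of the patients in the control group would experience mild, moderate, or severe dysphagia", and success is that figure being "improved to the point where just 20% of the patients are similarly affected". The first of three planned analyses is a discrete-time survival model: "we will look at the time-to-event where the event is" no dysphagia. The second is a repeated-measures ordinal model of steroid against control, with no baseline covariate named. The third is a comparison with the institution's previous three-dose study. Mann-Whitney tests of scores at each time point are also planned.

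The Subjects section sets eligibility by age and type of operation. Its exclusions include "those with a history of previous anterior cervical spine surgery, any patient requiring a halo vest, patients on chronic steroids", but not existing difficulty in swallowing. All three swallowing instruments, including Bazaz, are completed before surgery. Nothing in the document says how those baseline grades enter any analysis.

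The Potential Benefits section says the results will support steroids for "reducing the incidence and severity of dysphagia among patients undergoing anterior cervical spine surgery".

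**The concern.** The question is what a perioperative dose does to dysphagia after surgery, including its incidence. An absolute grade, in patients whose baseline status is unrestricted, measures prevalence at the time of asking. Two kinds of patient show the gap:

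- Mild before surgery and mild at two weeks: counted as affected, although the grade has not changed.
- Mild before surgery, worse afterwards, then back to a stable mild: never has the survival event and is censored at the last visit, although the patient has recovered to the pre-operative state.

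Dysphagia that was there before surgery and does not respond to the dose adds the same number of affected patients, on average, to each arm. That pulls the risk ratio towards 1, lowers power, and makes an absolute success level of 20% harder to reach. It also leaves open, until after unblinding, how such patients should be treated.

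**Working it through.** **Inputs from the plan.** Control 50%, steroid 20%, 32 per group, significance level 0.05 with sidedness not stated (Design and Subjects sections).

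**Assumed input.** b is the share of all patients with pre-operative dysphagia that is still present at two weeks whatever the arm. The documents give no value, so a range is used.

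**The plan's own figure.** The Design section claims that "32 patients in each group would give us 81% power to reject the null hypothesis". The pooled two-proportion formula at 50% versus 20% gives 82.1% one-sided and 72.1% two-sided. Exact binomial enumeration of the pooled z-test gives 82.1% and 73.4%. The stated 81% therefore fits a one-sided test. That is a separate matter; below, the exact two-sided test is held fixed so that any change is due to b or to the outcome definition.

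**Effect of b when 50% and 20% apply to patients without persistent pre-operative dysphagia.**

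- Absolute outcome: control b + (1−b)×0.50; steroid b + (1−b)×0.20.
- New-or-worsened outcome, if the persistent cases do not worsen: control (1−b)×0.50; steroid (1−b)×0.20.

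| b | Absolute outcome | Power | New or worsened | Power |
|---|---|---|---|---|
| 0 | 50% vs 20% | 73.4% | 50% vs 20% | 73.4% |
| 5% | 52.5% vs 24% | 67.6% | 47.5% vs 19% | 69.8% |
| 10% | 55% vs 28% | 62.3% | 45% vs 18% | 66.2% |
| 20% | 60% vs 36% | 52.3% | 40% vs 16% | 59.0% |

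The risk difference is 0.30×(1−b) under either definition: 27 points at b=10% and 24 points at b=20%. The risk ratio differs. For the absolute outcome it is 28/55 = 0.51 and 36/60 = 0.60; for new or worsened it stays at 0.40.

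**How much the redefinition recovers.**

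- b=10%: loss 73.4 − 62.3 = 11.1 points; recovered 66.2 − 62.3 = 3.9 points, or 35%.
- b=20%: loss 73.4 − 52.3 = 21.1 points; recovered 59.0 − 52.3 = 6.7 points, or 32%.

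If patients with pre-operative dysphagia worsen at the same rates as everyone else, new-or-worsened power at b=10% is 73%, so 66% is the lower end for that outcome.

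**Other reading of the 50%.** Suppose it already includes the persistent cases, and the planned 60% relative reduction (from 50 to 20) acts only on new cases. The steroid rate is then b + (0.50−b)×0.40: 26% at b=10% and 32% at b=20%. Exact two-sided power for the absolute outcome is 53% and 33%. The table therefore shows the milder case.

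**Reaching an absolute 20%.** Under the first reading, the rate needed in the remaining patients is (0.20−b)/(1−b): 0.10/0.90 = 11% at b=10%, and 0 at b=20%. Under the second, the share of new cases to be prevented is 1 − (0.20−b)/(0.50−b): 75% at b=10% and 100% at b=20%. On both readings, every new case must be prevented at b=20%, and the level cannot be reached only when b exceeds 20%.

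**The case against.** **The absolute comparison is valid as it stands.** Arms are randomised, so pre-operative dysphagia is balanced in expectation, and the contrast answers a fair question about dysphagia after the dose. This stands. A reader might infer systematic bias, but the documents do not support that; what remains is dilution, interpretation and chance imbalance in a small trial.

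**The success level is not shown to be unreachable.** A reader might infer that 20% cannot be attained. That needs b above 20%, and the documents give no prevalence. Excluding previous anterior cervical surgery removes one likely source of existing dysphagia. If b is 5%, the power loss is about 6 points.

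**The outcome definition does not cause the whole loss.** A reader might charge the full fall from 73% to 62% or 52% to the absolute definition. The working shows otherwise: redefinition leaves the risk difference unchanged and returns about a third of the lost power. The rest comes from enrolling these patients.

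**The two-week binary is a sizing outcome.** It is not among the three listed analyses. The Subjects section even justifies the same 32 per group differently: "With a power of 0.80 and a clinical meaningful difference of 30% in scores, an estimated 32 patients per group is needed". The ordinal model and the Mann-Whitney tests use scores, and in an ordinal model conditional on baseline a mild-to-mild patient is compared with similar patients. So a covariate does help there. It does not help the survival model, where the event itself leaves out return to a stable pre-operative grade.

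**A baseline-referenced outcome has costs.** Patients already severe cannot worsen, and a one-grade fluctuation on a four-grade scale can decide the result. These costs are real and belong in the plan.

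**Conclusion.** The concern holds as a gap between the stated question and the outcome definitions. It is clearest for the survival event, which never counts a patient who recovers to a stable pre-operative grade above none. The facts (no exclusion, a baseline grade collected, no stated use of it, absolute definitions) can be read directly from the document.

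The size is conditional. It rests on an assumed b, on persistence being the same in both arms, and on 50% versus 20% applying to the other patients. On those terms the absolute outcome costs about 11 points of exact two-sided power at b=10% and 21 at b=20%, and redefinition gives back about 4 and 7. If b is near zero, little changes numerically. The better reason to change is that the result would then answer the question about post-operative dysphagia; the power gain is modest. This is an inexpensive improvement to the plan and does not invalidate the trial.

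**What to change.** Before unblinding, amend the analysis text as follows:

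1. Define the discrete-time event as no dysphagia, or return to the patient's pre-operative Bazaz grade or better.
2. Define the two-week binary as a Bazaz grade worse than the patient's own pre-operative grade. Keep the absolute any-dysphagia proportion as a supportive outcome, for comparison with the literature figure.
3. Include the pre-operative grade as a covariate in the repeated-measures ordinal model.
4. Report, by arm, the number of patients with pre-operative dysphagia and the number already severe.

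No visit, instrument or patient is added, because the pre-operative Bazaz grade is already collected. There are two downsides to state in the plan: patients severe before surgery cannot meet the worsening definition, and the 50% planning rate applies directly only to the absolute outcome, so power for the new binary has to be shown over a stated range of b.
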